2.3.5 Potential Risks of Durvalumab + Tremelimumab in the Relevant Indication

Overall risks

Monoclonal antibodies may target several immune checkpoint proteins. These include programmed cell death ligand 1 (PD-L1), programmed cell death-1 (PD-1) or cytotoxic T-lymphocyte antigen-4 (CTLA-4). The anticipated result is an enhanced endogenous immune responses directed against tumor cells. However, there is the likelihood for adverse effects on other tissues as a consequence of stimulating the immune system.

Adverse drug reactions most seen with the immune checkpoint inhibitor class of agents are likely an outcome of the effects of inflammatory cells on specific tissues. These are generally events with a potential inflammatory or immune mediated mechanism and which may require more frequent monitoring and/or unique interventions such as immunosuppressants and/or endocrine therapy. Almost any organ system is susceptible to these immune mediated effects, and are most commonly seen as gastrointestinal AEs such as colitis and diarrhoea, pneumonitis/interstitial lung disease (ILD), hepatic AEs such as hepatitis and liver enzyme elevations, skin events such as rash and dermatitis and endocrinopathies including hypo- and hyper-thyroidism.

Durvalumab

The following are some risks associated with durvalumab: diarrhea/colitis and intestinal perforation, pneumonitis/ILD, endocrinopathies (hypo- and hyper-thyroidism, type I diabetes mellitus, hypophysitis and adrenal insufficiency) hepatitis/increases in transaminases, nephritis/increases in creatinine, pancreatitis/increases in amylase and lipase, rash/pruritus/dermatitis, myocarditis, myositis/polymyositis, other rare or less frequent inflammatory events including neurotoxicities, infusion-related reactions, hypersensitivity reactions and infections/serious infections.

Please refer to the current version of the durvalumab IB for information on all identified and potential risks with the drug.

In monotherapy clinical studies AEs (all grades) reported very commonly ($\geq 10\%$ of patients) are fatigue, nausea, decreased appetite, dyspnea, cough, constipation, diarrhea, vomiting, back pain, pyrexia, asthenia, anemia, arthralgia, peripheral edema, headache, rash, and pruritus. Approximately 9% of patients experienced an AE that resulted in permanent discontinuation of durvalumab and approximately 6% of patients experienced an SAE that was considered to be related to durvalumab by the study investigator.

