Lung or liver resection will be scheduled approximately 3-weeks after the infusion of the immunotherapeutic agents. Completing up to 4 months of chemotherapy after surgical resection instead of immunotherapy (durvalumab for cohort A, durvalumab/oleclumab for cohort B, or durvalumab/monalizumab for cohort C) continuation is an option depending on the preferences of the treating physician/patient (i.e., subjects can opt out of the planned post-operatively immunotherapy). Post-operative therapy will be either chemotherapy per physician/patient choice or 4months of immunotherapy. As synchronous primary lesions are allowed in this study, the appropriate clinical care as determined by the treating multidisciplinary team for addressing the primary lesion will be allowed. Though primary resection on clinical trial prior to liver resection will not be allowed, primary resection may be simultaneous with liver resection or occur after liver resection. In addition as short course radiation therapy (5 days) is often employed for rectal primaries this will be allowed in this clinical trial as long as radiation therapy is \geq 1 week from first dose of study treatment. Factoring the occurrence of potential immune mediated AEs prior to resection, an allowance of a 3-10 weeks from neoadjuvant therapy administration will be permitted to complete metastatic and/or primary resection

As the mechanism of action of immunotherapy should not impact wound healing, patients may start adjuvant therapy as early as 4 weeks after resection, per treating physician discretion, provided they have achieved adequate status after surgery (ex. Resolution of post-operative concerns). Post-operative therapy thus can begin between 4weeks to 12 weeks post-operatively. However, if patients require >12 weeks for postoperative recovery they will not be allowed to initiate adjuvant immunotherapy.

The study design schematic is below.

Study Schematic

5.1.1 Screening visit.

If a patient is thought to be a potential candidate for the trial, then he/she can be offered participation and, if agreeable, will undergo screening procedure outlined below from D-14 to D-1. Previously conducted HIV, PT/PTT, and hepatitis testing within 30 days does not need to be repeated and will be acceptable for screening purposes (tests performed at outside laboratories as standard of care testing will be accepted).

Table 5.1-1: Screening Procedural Outline

Procedure	Screening Visit From D-14 to D-1	Notes

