7. ADVERSE EVENTS: LIST AND REPORTING REQUIREMENTS

7.1 Definition of Adverse Events

The International Conference on Harmonisation (ICH) Guideline for Good Clinical Practice (GCP) E6(R1) defines an AE as:

Any untoward medical occurrence in a patient or clinical investigation subject administered a pharmaceutical product and which does not necessarily have a causal relationship with this treatment. An AE can therefore be any unfavorable and unintended sign (including an abnormal laboratory finding), symptom, or disease temporally associated with the use of a medicinal product, whether or not considered related to the medicinal product.

An AE includes but is not limited to any clinically significant worsening of a subject's preexisting condition. An abnormal laboratory finding (including ECG finding) that requires medical intervention by the investigator, or a finding judged by the investigator as medically significant should be reported as an AE. If clinical sequelae are associated with a laboratory abnormality, the diagnosis or medical condition should be reported (eg, renal failure, hematuria) not the laboratory abnormality (eg, elevated creatinine, urine red blood cells increased). Abnormal laboratory values that are not, in the investigator's opinion, medically significant and do not require intervention should not be reported as AEs.

Adverse events may be treatment emergent (ie, occurring after initial receipt of investigational product) or nontreatment emergent. A nontreatment-emergent AE is any new sign or symptom, disease, or other untoward medical event that begins after written informed consent has been obtained but before the subject has received investigational product. Elective treatment or surgery or preplanned treatment or surgery (that was scheduled prior to the subject being enrolled into the study) for a documented pre-existing condition that did not worsen from baseline is not considered an AE (serious or nonserious). An untoward medical event occurring during the prescheduled elective procedure or routinely scheduled treatment should be recorded as an AE or SAE.

The investigator (or physician designee) is responsible for verifying and providing source documentation for all adverse events and assigning the attribution for all adverse events for subjects enrolled.

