7.3 Definition of Adverse Events of Special Interest

An adverse event of special interest (AESI) is one of scientific and medical interest specific to understanding of the Investigational Product and may require close monitoring and rapid communication by the investigator to the supporting company. An AESI may be serious or non-serious. The rapid reporting of AESIs allows ongoing surveillance of these events in order to characterize and understand them in association with the use of this investigational product.

AESIs for durvalumab ±tremelimumab include but are not limited to events with a potential inflammatory or immune-mediated mechanism and which may require more frequent monitoring and/or interventions such as steroids, immunosuppressants and/or hormone replacement therapy. These AESIs are being closely monitored in clinical studies with durvalumab monotherapy and combination therapy. An immune-mediated adverse event (imAE) is defined as an AESI that is associated with drug exposure and is consistent with an immune-mediated mechanism of action and where there is no clear alternate etiology. Serologic, immunologic, and histologic (biopsy) data, as appropriate, should be used to support an imAE diagnosis. Appropriate efforts should be made to rule out neoplastic, infectious, metabolic, toxin, or other etiologic causes of the imAE.

If the Investigator has any questions in regards to an event being an imAE, the Investigator should promptly contact the Study Physician.

AESIs observed include:

- Fatigue / asthenia
- Pyrexia
- Diarrhea / Colitis

- Pneumonitis / Interstitial lung disease (ILD)
- ALT/AST increases / hepatitis / hepatotoxicity
- Neuropathy / neuromuscular toxicity (e.g. Guillain-Barré, and myasthenia gravis)
- Endocrinopathies (i.e. events of hypophysitis, hypopituitarism adrenal insufficiency, diabetes insipidus, hyper- and hypothyroidism and type I diabetes mellitus)
- Rash / Dermatitis
- Nephritis / Blood creatinine increases
- Pancreatitis (or labs suggestive of pancreatitis - increased serum lipase , increased serum amylase)
- Other inflammatory responses that are rare with a potential immune-mediated aetiology include, but are not limited to, myocarditis, pericarditis, and uveitis.
- AESI specifically related to Oleclumab (cohort B) include:::
 - Cardiac chest pain, transient ischemic attack, and thromboembolism
These are of interest due to the drug's risk of arterial calcifications, arterial ischemic disorder and thrombosis.

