5. More potent immunosuppressives should be considered for events not responding to systemic steroids (eg, infliximab, mycophenolate, etc).

If the investigator has any question in regards to an AE being an irAE, the investigator should immediately contact the medical monitor. Treatment modifications will not be required for AEs that are clearly not attributed to Durvalumab, tremelimumab, oleclumab or Monalizumab (such as an accident) or for laboratory abnormalities that are not deemed to be clinically significant.

Dose reductions of Durvalumab, tremelimumab, oleclumab or Monalizumab are not permitted.

Treatment modifications may be required for Durvalumab, tremelimumab, monalizumab, and oleclumab in the event of treatment-related toxicity. General guidelines regarding treatment modification are provided in Table 7.7.1 for all cohorts. In addition, management guidelines for adverse events of special interest (AESI) are detailed in Section 7.3. All toxicities will be graded according to NCI CTCAE v4.03 for cohort A and CTCAE v5.0 for cohorts B and C (CTCAE v5.0 is referenced in Table 7.7.1). In case of doubt, the investigator should consult with the medical monitor.

Table 7.7.1 Dosing Modification and Toxicity Management Guidelines

Dosing Modification and Toxicity Management Guidelines for Immune-Mediated, Infusion-Related, and Non-Immune-Mediated Reactions (Use for all Cohorts)

1 November 2017 (CTCAE Version 5.0)

General Considerations

Dose Modifications	Toxicity Management

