
Note: For Grade ≥ 3 asymptomatic amylase or lipase levels, hold study drug/study regimen, and if complete work up shows no evidence of pancreatitis, study drug/study regimen may be continued or resumed.
 
Note: Study drug/study regimen should be permanently discontinued in Grade 3 events with high likelihood for morbidity and/or mortality – e.g., myocarditis, or other similar events even if they are not currently noted in the guidelines. Similarly, consider whether study drug/study regimen should be permanently discontinued in Grade 2 events with high likelihood for morbidity and/or mortality – e.g., myocarditis, or other similar events even if they are not currently noted in the guidelines – when they do not rapidly improve to Grade <1 upon treatment with systemic steroids and following full taper
 
Note: There are some exceptions to permanent discontinuation of study drug for Grade 4 events (i.e., hyperthyroidism, hypothyroidism, Type 1 diabetes mellitus).
	
– when these events are not responding to systemic steroids.– With long-term steroid and other immunosuppressive use, consider need for Pneumocystis jirovecii pneumonia (PJP, formerly known as Pneumocystis carinii pneumonia) prophylaxis, gastrointestinal protection, and glucose monitoring.– Discontinuation of study drug/study regimen is not mandated for Grade 3/Grade 4 inflammatory reactions attributed to local tumor response (e.g., inflammatory reaction at sites of metastatic disease and lymph nodes). Continuation of study drug/study regimen in this situation should be based upon a benefit-risk analysis for that patient.

Specific Immune-Mediated Reactions

Adverse Events	Severity Grade of the Event (NCI CTCAE version5.0)	Dose Modifications	Toxicity Management
Pneumonitis/Interstitial Lung Disease (ILD)	Any Grade	General Guidance	For Any Grade:
			
 – Monitor patients for signs and symptoms of pneumonitis or ILD (new onset or worsening shortness of breath or cough). Patients should be evaluated with imaging and pulmonary function tests, including other diagnostic procedures as described below. – Initial work-up may include clinical evaluation, monitoring of oxygenation via pulse oximetry (resting and exertion), laboratory work-up, and high- resolution CT scan.

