Laboratory	X	X	X	X	X	X	CBC w/differential and platelet count, LFTs (ALT, AST, total bilirubin, alkaline phosphatase), BUN or serum urea level, creatinine, Ca, Mg, Na, K, Cl, glucose)
CEA	X			X		X	
TSH/FT4	X			X			
Lipase/amylase	X						
Immunogenicity Assessments, Peripheral Blood	X				X	X (at first visit only)	

Pregnancy test (WOCBP only)		X	As indicated clinically						Serum or urine pregnancy test to be done within 72 hours of dose				
ECOG PS	X	X	X	X	X			see appendix 1					
Adverse Events Assessment	X	X	X	X	X			Per CTCAE v4.03 for Cohort A and v5.0 for Cohorts B and C					
CT C/A/P with IV contrast with tumor measurements					X	X							
Immunogenicity Assessments, Peripheral Blood	Up to 12 tubes of blood with 5ml each will be collected for immunological assessment. For specific details see laboratory manual (up to 4 missed blood draws are allowed)												
	
CEA: Carcioembryonic Antigen; ECOG PS: Eastern Cooperative Oncology Group Performance Status; TSH: Thyroid stimulating hormone; FT4: Free T4; WOCBP: Women of child bearing potential; CT C/A/P: CT scan chest, abdomen and pelvis
 
Toxicity 30 day f/u can happen 30 days (+/- 2 weeks) after last treatment dose and this can be done by phone call.
 
Note after one year of follow-up without recurrence schedule of follow-ups can be adjusted according to standard of care. This will take precedence over the study calendar.
												

Table 10.3 Post-Resection Study Calender for Cohorts (B and C)

TIME PERIOD	Post-operative evaluation	Wk	Wk	Comment							
	1 (same day as Durvalumab)	3	5	7	9	11	13	15	every 4 months		
	(0.5-2wks post surgery)	+/-3d	+/-6 weeks								
PROCEDURE											
Durvalumab		X		X		X		X			
Oleclumab (cohort B)		X	X	X	X	X	X	X			If patient requires >12 weeks for postop recovery, they will not be initiated on adjuvant immunotherapy
Monalizumab (cohort C)		X		X		X		X			
Clinic Visit		X	X	X	X	X	X	X	X		
Physical Examination		X	X	X	X	X	X	X	X		
Vital Signs		X	X	X	X	X	X	X	X		Including BP, HR,

										temperature
Review of Concomitant Medication		X	X	X	X	X	X	X	X	
Laboratory		X	X	X	X	X	X	X	X	CBC w/differential and platelet count, LFTs (ALT, AST, total bilirubin, alkaline phosphatase), BUN or serum urea level, creatinine, Ca, Mg, Na, K, Cl, glucose)
CEA	X								X	X
TSH/FT4	X			X		X		X		
Lipase/amylase	X									
Immunogenicity Assessments, Peripheral Blood	X			X				X		X (at first visit only)

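### No lipase/amylase test is scheduled once adjuvant immunotherapy starts, so the hold for silent Grade 3 or higher elevations depends on an unscheduled test (minor, cheap to fix)

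*Combined protocol and SAP*

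**What the plan says.** **Schedule.** Table 10.1 has lipase and amylase at screening and at the visit before resection. After resection, Table 10.2 (Cohort A) and Table 10.3 (Cohorts B and C) each give the row "Lipase/amylase" a single mark, at the post-operative evaluation 0.5 to 2 weeks after surgery. The routine laboratory panel repeated at adjuvant visits covers blood counts, liver tests, renal tests, electrolytes and glucose, but neither of these two analytes. TSH/FT4, in the neighbouring row, does continue on treatment: Week 9 in Table 10.2, and Weeks 5, 9 and 13 in Table 10.3.

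**Adjuvant start.** Section 5.1 states: "Post-operative therapy thus can begin between 4weeks to 12 weeks post-operatively". Immunotherapy is not compulsory. The same section allows the alternative "Completing up to 4 months of chemotherapy after surgical resection instead of immunotherapy".

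**Why the value matters to the protocol.** For Grade 3 or higher, the general notes of Table 7.7.1 read "asymptomatic amylase or lipase levels, hold study drug/study regimen, and if complete work up shows no evidence of pancreatitis", after which dosing may go on. Section 7.3 lists among the adverse events of special interest (AESIs) "Pancreatitis (or labs suggestive of pancreatitis - increased serum lipase , increased serum amylase". Section 2.3.5 names "pancreatitis/increases in amylase and lipase" as a durvalumab risk, and durvalumab is in every cohort's adjuvant regimen.

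**Limits the protocol sets.** Section 7.1 excludes from reporting those laboratory results that the investigator does not consider "medically significant and do not require intervention should not be reported as AEs". Section 7.7 asks for no treatment change for events clearly unrelated to study drug "or for laboratory abnormalities that are not deemed to be clinically significant". Sections 13.3.2 and 13.3.3 leave asymptomatic Grade 3 or 4 lipase or amylase elevations out of both TOX and TOXpost.

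**The concern.** The hold in Table 7.7.1 concerns elevations without symptoms, so neither the clinic visit nor the examination can set it off. It needs a result. Once adjuvant dosing has begun, no calendar visit supplies one.

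Two things are at stake, both modest. For the individual patient, later doses may be given on top of an elevation that the protocol wants worked up first. For the trial, safety is a primary endpoint (Section 13.1) and adverse events will be tabulated (Section 13.4). A table with no lipase or amylase events during adjuvant treatment could then mean that none occurred or that nobody looked.

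**Working it through.** **1. The plan's own figures.** The plan states no expected number of lipase or amylase events. Its nearest figure is the TOXpost rule of Section 13.3.3: prior Beta(0.4, 1.6), stop if Pr(rate > 0.20 | data) > 0.90. Recomputing it gives the stated boundaries (2/3, 3/6, 4/9, 5/13, 6/17, 7/21, 8/25). At a true rate of 0.20 it also gives the stated stopping probabilities of 0.25 (N = 25) and 0.20 (N = 15). Because asymptomatic elevations are excluded from TOXpost, more testing for them leaves these figures unchanged.

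**2. Timing** (Section 5.1, Tables 10.2 and 10.3). The columns of Table 10.3 can be aligned by its durvalumab row, which is marked at Weeks 1, 5, 9 and 13.
- Last scheduled test to first adjuvant dose: shortest 4 − 2 = 2 weeks, longest 12 − 0.5 = 11.5 weeks.
- Period in which a hold can act, first to last durvalumab dose: Week 1 to Week 13 = 12 weeks, with 0 scheduled tests.
- Doses given after adjuvant exposure without a scheduled test: durvalumab 3 of 4, oleclumab 6 of the 7 marked, monalizumab 3 of 4.

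**3. Event rate.** Section 2.5.4 reports one subject with a treatment-related Grade 3/4 lipase increase on durvalumab plus oleclumab. Section 2.5.3 gives the denominator: 24 (escalation) + 50 (expansion) = 74. This agrees with the percentages in Section 2.5.4: 19/74 = 25.7% for fatigue and 4/74 = 5.4% for Grade 3 or 4 anemia.
- Rate: 1/74 = 1.35%; exact (Clopper-Pearson) 95% interval 0.034% to 7.30%.

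**4. Expected events.** Section 13.2 takes 12 of 15 patients per cohort reaching surgery.

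| Patients starting adjuvant immunotherapy | Expected Grade 3/4 lipase events | Chance of none |
|---|---|---|
| Cohort B, all 12 | 12/74 = 0.16 | (73/74)^12 = 85% |
| Cohort B, half choose chemotherapy (assumption) | 6/74 = 0.08 | not computed |
| Cohorts B and C, all 24 (rate extended to C by assumption) | 24/74 = 0.32 | (73/74)^24 = 72% |

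Over the interval for the rate, the figure for 24 patients runs from 24 × 0.00034 = 0.01 to 24 × 0.0730 = 1.75.

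**5. What these numbers count.** They count all treatment-related Grade 3/4 lipase events, with or without symptoms. The source does not give symptom status. Missed silent events would be some fraction of them.

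**The case against.** The strongest reply is that this is a choice, not an oversight. The calendar decides row by row what to repeat, and it repeats thyroid tests but not pancreatic enzymes. The protocol gives silent elevations little weight throughout. They do not count as TOX or TOXpost, modest ones need no steroids, dosing may resume if work-up finds no pancreatitis, and results judged unimportant are neither reported nor acted on. Section 7.3 describes the management guidelines as an aid to clinical judgement, so Table 7.7.1 tells the investigator what to do with a value and does not promise to look for one. Adjuvant dosing visits include examination and adverse event assessment, so symptomatic pancreatitis would still be sought. Tests before surgery and after it also give the hold scheduled triggers following the neoadjuvant dose.

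Much of this stands, and it is why the point is minor. Two parts do not carry the conclusion. No section says that the omission is deliberate or gives a reason for it. And low weight in the stopping rules does not cancel the instruction to hold drug pending work-up. Whether a result is clinically significant can be judged only once there is a result.

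The objection is also right about size. The 1/74 is a treatment-related rate from a different combination than Cohort C's. Section 2.4.4 reports all 23 monalizumab-related events as Grade 1 or 2 and names no lipase event. The 0.32 further assumes that nobody reaching surgery chooses chemotherapy.

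**Conclusion.** The gap is real and minor. From adjuvant Week 1 to Week 13, an existing safety hold for a listed AESI has no scheduled trigger. The expected number of treatment-related Grade 3/4 lipase events is about 0.16 in Cohort B, and at most about 0.32 (0.01 to 1.75) in Cohorts B and C together. This rests on one event in 74 subjects with advanced disease and different dosing, on all patients reaching surgery starting immunotherapy, and on carrying the rate over to Cohort C. It is an upper guide for missed silent events.

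A reader might infer more than the documents support:
- **That the stopping rules or the feasibility result are compromised.** They are not. Asymptomatic elevations are excluded from TOX and TOXpost, and feasibility is whether the patient reaches surgery.
- **That the relevant untested period is about 25 weeks.** Adverse event collection does run a further 90/7 = 12.9 weeks after the last durvalumab dose, making 24.9 weeks. But no hold can act in that second part, and the proposed tests do not reach it.
- **That the Grade 3/4 lipase elevation in Section 2.6 shows that silent values get recorded as adverse events, or gives a usable adjuvant rate.** Neither its symptoms nor its phase is stated. It arose in Cohort A, where tremelimumab is given before surgery but not afterwards.

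**What to change.** Add lipase and amylase to the existing blood draws at Weeks 1, 5, 9 and 13 in Table 10.3, and in Table 10.2 for any Cohort A patients still to reach those visits. Week 1 serves as a fresh pre-dose baseline; Weeks 5, 9 and 13 are the on-treatment tests. When reporting this AESI, give the number of patients tested during adjuvant treatment. For patients already past these visits, state that it was not systematically assessed.

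The cost is two analytes on blood already being drawn. The downside is a few extra work-ups and temporary holds, some for values that will prove harmless. The change to Table 10.2 will reach few patients, because Section 13.2 expected Cohort A to have enrolled about 25, its full number, when this revision was approved. If the omission was intended, one sentence giving the reason would also settle the point, though the reporting statement would still be needed.
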